10.2.2. Serious Adverse Event

An SAE is any untoward medical occurrence that at any dose:

- Results in **death** – includes all deaths, even those that appear to be completely unrelated to study drug (eg, a car accident in which a participant is a passenger).
- Is **life-threatening** – in the view of the investigator, the participant is at immediate risk of death at the time of the event. This does not include an AE that had it occurred in a more severe form, might have caused death.
- Requires in-patient **hospitalization or prolongation of existing hospitalization**. Inpatient hospitalization is defined as a hospital admission (any duration) or an emergency room visit for longer than 24 hours. Prolongation of existing hospitalization is defined as a hospital stay that is longer than was originally anticipated for the event or is prolonged due to the development of a new AE as determined by the investigator or treating physician.
- Results in persistent or significant **disability/incapacity** (substantial disruption of one's ability to conduct normal life functions).
- Is a **congenital anomaly/birth defect**
- Is an **important medical event** - Important medical events may not be immediately life-threatening or result in death or hospitalization but may jeopardize the participant or may require intervention to prevent one of the other serious outcomes listed above (eg, intensive treatment in an emergency room or at home for allergic bronchospasm; blood dyscrasias or convulsions that do not result in hospitalization; or development of drug dependency or drug abuse).

Criteria for reporting SAEs must be followed for these events.

10.2.3. Adverse Events of Special Interest

An AESI (serious or non-serious) is one of scientific and medical interest specific to the sponsor's product or program, for which ongoing monitoring and rapid communication by the investigator to the sponsor can be appropriate. Such an event might warrant further investigation in order to characterize and understand it.

10.2.4. Infusion Reactions

Infusion reactions are defined as any relevant AE that occurs during the infusion or within 2 hours after the infusion is completed.

10.2.5. Severity

The severity of AEs will be graded according to the following scale:

Mild: Does not interfere in a significant manner with the participant normal functioning level. It may be an annoyance. Prescription drugs are not ordinarily needed for relief of symptoms but may be given because of personality of the participant.

Moderate: Produces some impairment of functioning but is not hazardous to health. It is uncomfortable or an embarrassment. Treatment for symptom may be needed.

Severe: Produces significant impairment of functioning or incapacitation and is a definite hazard to the subject's health. Treatment for symptom may be given and/or participant hospitalized.

If a laboratory value is considered an AE, its severity should be based on the degree of physiological impairment the value indicates.

Infusion Reactions

The severity of infusion reactions will be graded according to the following scale (semi-colon indicates "or" within description of the grade):

Mild: Mild transient reaction; infusion interruption not indicated; intervention not indicated.

Moderate: Therapy or infusion interruption indicated but responds promptly to symptomatic treatment (eg, antihistamines, NSAIDs, narcotics, IV fluids); prophylactic medications indicated for ≤ 24 hours.

Severe: Prolonged (eg, not rapidly responsive to symptomatic medication and/or brief interruption of infusion); recurrence of symptoms following initial improvement; hospitalization indicated for clinical sequelae; life-threatening consequences; urgent intervention indicated; death.

Injection Site Reactions

The severity of injection site reactions will be graded according to the following scale (semi-colon indicates "or" within description of grade):

Mild: Pain that does not interfere with activity; mild discomfort to touch; < 5 cm of erythema or induration that does not interfere with activity

Moderate: Pain that requires repeated use of non-narcotic pain reliever > 24 hours or interferes with activity; discomfort with movement; 5.1 cm to 10 cm erythema or induration or induration that interferes with activity

Severe: Pain that requires any use of narcotic pain reliever or that prevents daily activity; significant discomfort at rest; >10 cm erythema or induration; prevents daily activity; requires ER visit or hospitalization; necrosis or exfoliative dermatitis

10.2.6. Causality

The investigator must provide causality assessment as whether or not there is a reasonable possibility that the drug caused the adverse event, based on evidence or facts, his/her clinical judgment, and the following definitions. The causality assessment must be made based on the available information and can be updated as new information becomes available.

The following factors should be considered when assessing causality:

- Temporal relationship: time to onset vs time drug was administered
- Nature of the reactions: immediate vs. long term
- Clinical and pathological features of the events
- Existing information about the drug & same class of drugs
- Concomitant medications
- Underlying and concurrent illnesses
- Response to dechallenge (drug discontinuation) or dose reduction
- Response to rechallenge (re-introduction of the drug) or dose increase, when applicable
- Patient's medical and social history

Causality to the study drug (including study drug administration):

- Related:
 - The AE follows a reasonable temporal sequence from study drug administration and cannot be reasonably explained by the nature of the reaction, patient's clinical (eg, disease under study, concurrent diseases, concomitant medications), or other external factors.
- or
- The AE follows a reasonable temporal sequence from study drug administration and is a known reaction to the drug under study or its class of drugs or is predicted by known pharmacology.
- Not Related:
 - The AE does not follow a reasonable sequence from study drug administration or can be reasonably explained by the nature of the reaction, patient's clinical state (eg, disease under study, concurrent diseases, and concomitant medications) or other external factors.

Causality to the study conduct (protocol specified procedure):

- Related:

- The AE follows a reasonable temporal sequence from a protocol specified procedure and cannot be reasonably explained by the nature of the reaction, patient's clinical (eg, disease under study, concurrent diseases, concomitant medications), or other external factors.
- Not Related:
 - The AE does not follow a reasonable sequence from a protocol specified procedure or can be reasonably explained by the nature of the reaction, patient's clinical state (eg, disease under study, concurrent diseases, and concomitant medications) or other external factors.

10.3. Safety Monitoring

The investigator will monitor the safety of study participant at his/her site(s) as per the requirements of this protocol and consistent with current Good Clinical Practice (GCP). Any questions or concerns should be discussed with the sponsor in a timely fashion. The sponsor will monitor the safety data from across all study sites. The Medical/Study Director will have primary responsibility for the emerging safety profile of the compound, but will be supported by other departments (eg, Global Patient Safety; Biostatistics and Data Management). Safety monitoring will be performed on an ongoing basis (eg, individual review of SAEs) and on a periodic cumulative aggregate basis.

10.4. Notifying Health Authorities, Institutional Review Board /Ethics Committee, and Investigators

During the study, the sponsor and/or the contract research organization (CRO) will inform health authorities, IECs/IRBs, and the participating investigators of any SUSARs (Suspected Unexpected Serious Adverse Reactions) occurring in other study centers or other studies of the active study drug (REGN9933; an FXI binder), as appropriate per applicable reporting requirements, including Regulation EU No 536/2014. In addition, the sponsor and/or CRO will comply with any additional local safety reporting requirements. All notifications to investigators will contain only blinded information.

Upon receipt of the sponsor's notification of a SUSAR that occurred with the study drug, the investigator will inform the Institutional Review Board (IRB)/Ethics Committee (EC) unless delegated to the sponsor.

Event expectedness for REGN9933 is assessed against the Reference Safety Information section of the Investigator's Brochure that is effective for expedited safety reporting.

Event expectedness for enoxaparin and apixaban is assessed against the SmPC.

At the completion of the study, the sponsor will report all safety observations made during the conduct of the trial in the CSR to health authorities and IECs/IRB as appropriate.

11. STATISTICAL PLAN

11.1. Statistical Hypothesis

The clinical hypothesis comparing the efficacy of REGN9933 to enoxaparin or apixaban will be assessed through a Bayesian estimation framework. Bayesian posterior probabilities will be reported to estimate the incidence of confirmed VTE for participants treated with REGN9933 and enoxaparin, as well as the odds ratio (OR) of confirmed VTE in participants administered REGN9933 as compared to that of enoxaparin (OR_{RE}). The statistical hypothesis is $OR_{RE} < 1$.

Specifically, the following will be reported:

- Probability that REGN9933 has a lower incidence of confirmed VTE through day 12 as compared to enoxaparin, ie the probability that the OR of VTE in REGN9933 versus enoxaparin, $Pr(OR_{RE} < 1)$. Other quantities will be used to estimate the magnitude of effect, eg $P(OR_{RE} < 0.5, 0.8, 0.9, \text{etc.} | \text{data})$

11.2. Justification of Sample Size

Up to total of approximately 360 participants will be randomized in a 1:1:1 allocation ratio to REGN9933, apixaban or enoxaparin. Each arm will have an approximate number of 120 participants.

The sample size was determined using the following assumptions:

- The event rate of VTE for REGN9933 was assumed to be 13% and was set to be 22.4% for enoxaparin ([Verhamme, 2021](#)) ([Weitz, 2020](#)).
- The prior distribution of the treatment difference, was assumed to be $\log(OR) \sim N(0, 0.843)$, which was expressed as the log(OR). The prior distribution follows a normal distribution centered around no treatment difference and with a variance such that extreme treatment differences are expected to be unlikely, ie, the probability that OR is between 0.25 and 4 is 90%.

Using these assumptions, and for the purpose of choosing a sample size, the following quantities were simulated:

- The probability of any beneficial effect of REGN9933 over enoxaparin, ie, the posterior distribution of the odds ratio comparing REGN9933 to enoxaparin of confirmed VTE. A beneficial effect is where $OR_{RE} < 1$, and thus the study will estimate $P(OR_{RE} < 1 | \text{data})$.
- In 75% of the simulated trials, in studies where the $P(OR_{RE} < 1 | \text{data}) > 0.95$, the sample size was 120 participants or less. Therefore, a sample size of 120 subjects per group was chosen.

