7.4. Replacement of Participants

Participants prematurely withdrawn from the study can be replaced, if needed, to ensure an adequate number of evaluable participants. The Medical/Study Director, in cooperation with the Study Biostatistician, will decide whether or not to replace a withdrawn participant.

Participants enrolled and withdrawn from study any time prior to first dose of study drug will not be considered evaluable for assessment and will be replaced with another participant. All participants who have received a dose of study drug will be included in an as treated analysis.

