9.2.2. Efficacy Procedures

9.2.2.1. Venography of the Operated Leg

Unilateral venography of the operated leg will be performed on day 10 (± 2 days). Detailed instructions for performing the venography are provided in the Study Imaging Manual for Venography and Event Reporting.

If DVT or PE is suspected at any point during the study, objective confirmatory testing should be carried out as described in Section 9.2.2.2. If the confirmatory tests do not demonstrate DVT/PE, or if a distal DVT is demonstrated by ultrasound, then venography on day 10 (± 2 days) should be performed as specified in the protocol. On the other hand, if the presence of DVT (if diagnosed by ultrasound, then DVT must be proximal) or PE is confirmed prior to the protocol-defined venogram on day 10 (± 2 days), then the venogram is not performed.

Venograms of low quality and/or venograms with imaging artifacts that cannot be used to confirm presence or absence of DVT will be labeled “non-evaluable”. Examples of reasons that contribute to low image quality or artifact include insufficient contrast filling and poor exposure. Detailed instructions for labeling non-evaluable images are provided in the Site Manual for Venography and Event Reporting.

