11.5. Interim Analysis

An IA will be conducted by the sponsor when there are at least 50 participants per arm who have finished the study. The timing of IA was determined for the minimal number of subjects required to observe a high probability that REGN9933 reduced confirmed VTE relative to enoxaparin, ie the smallest sample size where the posterior probability could be at least 90%, ie, $\text{Pr}(\text{OR}_{\text{RE}} \leq 1 | \text{data}) \geq 90\%$.

The IA will only be used for administrative purpose and will not be used to make any decisions regarding the conduct of this study, eg, to stop the study.

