2.2. Sample Size and Power Considerations

Approximately 360 participants will be randomized in a 1:1:1 allocation ratio to REGN9933, apixaban or enoxaparin. Each arm will have approximately 120 participants.

The sample size was determined through Bayesian approach. The treatment difference was expressed as the log(OR), and the prior distribution of the treatment difference was assumed to be $N(0,0.843)$, which follows a normal distribution centered around no treatment difference and with a variance such that extreme treatment differences are expected to be unlikely, i.e., 90% probability that OR is between 0.25 and 4.0.

The probability of any beneficial effect of REGN9933 over enoxaparin can be assessed by the posterior distribution of the odds ratio comparing REGN9933 to enoxaparin of confirmed VTE. A beneficial effect is where $OR_{RE} < 1$, and thus the study will estimate $Prob(OR_{RE} < 1 | \text{data})$.

The sample size of 120 patients per arm was determined through 10000 trial simulation, assuming confirmed VTE event rates of 13% for REGN9933 and 22.4% for enoxaparin. (Enoxaparin rates taken from [\(Verhamme, 2021\)](#) [\(Weitz, 2020\)](#)). Out of the 10000 simulated trials, 75% of the simulated trials with $Prob(OR_{RE} < 1 | \text{data}) > 0.95$ have the sample size of 120 or less.

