3.1. Efficacy Analysis Set

The primary analysis will be conducted in the modified intention to treat population (mITT) population, consisting of randomized and treated participants that have either an evaluable venogram, a confirmed episode of venous thromboembolism, or both through day 12. It is based on the treatment allocated (as randomized).

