5.7.1. Analysis of Primary Efficacy Variable

The primary analysis is to evaluate the efficacy of REGN9933 for the prevention of VTE after unilateral TKA, compared to enoxaparin. The primary efficacy variable is a binary indicator whether a participant has an adjudicated, confirmed VTE through day 12.

For any participant i , let p_i denote the VTE probability, trt_i denote the treatment assignment (0: enoxaparin, 1: REGN9933, 2: apixaban), $country_i$ denote the country indicator (1, 2, .., K), and age_grp_i be the age group indicator (0: $age < 70$ and 1: $age \geq 70$).

The following Bayesian logistic regression model adjusted by stratification factors (country and age group) is specified to compare the event rates of VTE among enoxaparin, REGN9933, and apixaban:

$$logit(p_i) = \beta_0 + \beta_1 * I(trt_i = 1) + \beta_2 * I(trt_i = 2) + \sum_{k=1}^{K-1} \theta_k * I(country_i = k) + \gamma * age_grp_i$$

where β_0 is the log odds of the VTE rate from enoxaparin, β_1 is the log odds ratio of REGN9933 relative to enoxaparin, and β_2 is the log odds ratio of apixaban relative to enoxaparin after adjustment by country and age group. The benefit of the treatment effect of REGN9933 over enoxaparin is expressed in terms of the odds ratio ($=e^{\beta_1}$) that is less than 1.

A weak prior $N(0,0.843)$ is chosen for parameters β_1 and β_2 . With this weak prior, the extreme treatment difference is unlikely, i.e., the probability of the odd ratio between 0.25 and 4 is around 90%. A vague prior $N(0,10^4)$ is used for the other regression parameters.

The treatment effect will be estimated using the Markov Chain Monte Carlo (MCMC) method via PROC BGLIMM in SAS. The SAS code for implementing the Bayesian logistic regression model is provided in Appendix [11.4.1](#)

Bayesian summary statistics (posterior mean and median, and two-sided 90% credible interval) of the treatment effect of REGN9933 vs enoxaparin (odds ratio = e^{β_1}) will be reported.

Based on the logistic regression model, the treatment effect (odds ratio = $e^{\beta_1 - \beta_2}$) of REGN9933 vs apixaban and the treatment effect (odds ratio = e^{β_2}) of apixaban vs enoxaparin will be reported. Their credible interval such as two sided 90% credible interval will also be reported.

The probability-based quantities for the magnitude of treatment effect at thresholds of clinical interest may be provided, e.g., $Prob(OR < 0.5, 0.8, 0.9, \text{etc.} | \text{data})$.

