5.7.5. Multiplicity Control

As the statistical inference for this study is to focus on estimation rather than testing a formal hypothesis and the Bayesian analysis is performed, the multiplicity adjustments of the different comparisons between groups will not be done.

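### The 75% that justifies 120 per arm is not the chance that this fixed design reaches P(OR_RE<1|data)>0.95; on the plan's own inputs that chance is about 57%

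*Protocol*

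**What the plan says.** Protocol 11.2 assumes VTE rates of 13% on REGN9933 and 22.4% on enoxaparin, with a N(0, 0.843) prior on log(OR). Among simulated trials with P(OR_RE<1|data)>0.95, it reports that in 75% "the sample size was 120 participants or less. Therefore, a sample size of 120 subjects per group was chosen". The synopsis has the same sentence. SAP 2.2, headed as sample size and power considerations, puts it this way: "Out of the 10000 simulated trials, 75% of the simulated trials with" a posterior above 0.95 had 120 or fewer. No other reason for 120 per arm is given.

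Other parts of the plan bear on how that figure can be read:

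- **Interim analysis (Protocol 11.5).** The interim "will not be used to make any decisions regarding the conduct of this study, eg, to stop the study". SAP 7 agrees that it is administrative.
- **Primary analysis set (SAP 3.1).** The mITT set is defined as "consisting of randomized and treated participants that have either an evaluable venogram, a confirmed episode of venous thromboembolism, or both through day 12".
- **Unreadable images (Protocol 9.2.2.1).** "Venograms of low quality and/or venograms with imaging artifacts that cannot be used to confirm presence or absence of DVT" are to be labelled non-evaluable.
- **Replacement (Protocol 7.4).** Participants withdrawn early "can be replaced, if needed, to ensure an adequate number of evaluable participants". Unreadable venograms are not mentioned.
- **Primary model (SAP 5.7.1).** A three-arm "Bayesian logistic regression model adjusted by stratification factors (country and age group").
- **Inference (SAP 5.7.5).** "the statistical inference for this study is to focus on estimation rather than testing a formal hypothesis".

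**The concern.** The sentence treats sample size as an outcome of each simulated trial. The natural reading is that accumating data were examined repeatedly, that the size at which the posterior first passed 0.95 was recorded, and that 120 is the 75th percentile of that size, possibly only among trials that passed. This is inference, because the look schedule, the maximum size and the denominator are not reported.

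A trial that stops at first crossing has many chances to pass. This trial has one, at its planned final size. The two probabilities differ, and conditioning on having crossed raises the first one further. A reader who meets 75% in a sample size and power section will probably take it as the chance that the study reaches the threshold it was sized on.

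There is a second gap. About 360 participants are to be randomised, but the primary analysis uses only those with an evaluable outcome. The text does not say which of these the simulated 120 refers to, and it states no loss rate or inflation.

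**Working it through.** **Inputs.** Rates 13% and 22.4% (Protocol 11.2). Prior log(OR) ~ N(0, 0.843) (Protocol 11.2, SAP 2.2). Vague intercept prior (SAP 5.7.1). Threshold 0.95. 120 per arm, 1:1 for the two arms compared.

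**Scale of the prior.** P(0.25<OR<4) = 2Φ(ln 4 / SD) − 1.
- 0.843 as SD: 90.0%, which is the plan's 90%.
- 0.843 as variance (SD 0.918): 86.9%.

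SD is therefore the main reading. Both are carried below.

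**Can the 75% be reproduced?** Not as a fixed-size probability. As a first-crossing share it can, under particular rules. In 10,000 simulated trials with looks every 1, 5, 10 or 20 per arm:

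| Quantity | Result |
|---|---|
| Crossed 0.95 at or before 120 per arm, all trials | 71%, 69%, 67%, 64% |
| Same, among trials crossing by 150 per arm | 88–90% |
| Same, among trials crossing by 200 per arm | 76–81% |
| Same, among trials crossing by 240 per arm | 72–77% |

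So 75% is attainable as a conditional share for some caps and look schedules. It is not shown to be miscalculated. It is a different quantity whose inputs are not reported.

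**Fixed design, by hand (normal approximation).**
- ln OR = ln[(0.13/0.87)/(0.224/0.776)] = −0.658 (OR 0.518).
- Sampling variance v = 1/(120×0.13×0.87) + 1/(120×0.224×0.776) = 0.1216, so SE = 0.349.
- Prior variance 0.843² = 0.711. Shrinkage k = 0.711/(0.711+0.1216) = 0.854. Posterior SD = √(0.854×0.1216) = 0.322.
- The posterior passes 0.95 when the estimate is below −1.645×0.322/0.854 = −0.621.
- Probability = Φ[(−0.621+0.658)/0.349] = Φ(0.108) = 54%.

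**Fixed design, exact.** Enumerate Binomial(n, 0.224) × Binomial(n, 0.13), compute P(OR<1|data) for each outcome on a numerical grid, and add up the probability of outcomes above 0.95:

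| Evaluable per arm | SD 0.843 | Variance 0.843 |
|---|---|---|
| 120 | 56.8% | 57.1% |
| 108 (10% lost) | 51.9% | 53.1% |
| 96 (20% lost) | 47.6% | 47.7% |
| 84 (30% lost) | 41.6% | 43.3% |
| about 187 (SD) or 185 (variance) | 75% | 75% |

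The loss rates are assumed, because the documents give none. The loss rows also assume equal loss in both arms and unchanged event rates among those retained.

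**Cross-checks at 120 per arm.**
- Flat prior on log(OR): 61.7%.
- Threshold 0.90 instead of 0.95: 71.0%.
- Frequentist power, one-sided 5%: pooled rate 0.177, null SE √(2×0.177×0.823/120) = 0.0493, alternative SE √[(0.13×0.87+0.224×0.776)/120] = 0.0489; Φ[(0.094−1.645×0.0493)/0.0489] = 60%.

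**Does covariate adjustment close the gap?** A three-arm logistic model with the SAP 5.7.1 priors, country and age group was run with a normal-approximation posterior and 12,000 trials per scenario. The assumptions, none from the documents, were 6 or 10 countries, country effects from 0 to ±1 log-odds, an age effect of 0 or 0.5, 40% aged 70 or over, and an 18% apixaban rate. Adjusted results were 54.6%, 55.1%, 57.4% and 55.2%; unadjusted results with the same approximation were 55.5%, 55.3%, 54.4% and 54.7%. It does not.

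**The case against.** The strongest reply is that nothing has been miscalculated. The documents never call the 75% power; SAP 2.2 words it as a conditional share, and such a share can equal 75%. Protocol 11.5 chooses the interim size by similar reasoning, as the smallest size at which a posterior threshold could be met, so the approach is at least consistent. The framework is estimation, 0.95 is not a success criterion, and expected interval width would be an equally natural basis for sizing. The trial is also not strictly fixed: enrolment is up to about 360, the IDMC may recommend stopping, and the sponsor may terminate for efficacy or futility. Finally, 57% comes from a simpler model than the planned one, and the loss rates are assumed.

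Much of this stands. The 75% is not an arithmetic slip, and the consequence is limited to how the sample size is justified. But the sponsor chose the 0.95 threshold for sizing and derived 120 from it, so the chance of reaching it is the relevant property of the design. None of the IDMC or sponsor termination provisions is a rule to stop on crossing 0.95, so none makes the 75% apply. The simpler model is not what drives the gap.

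**Conclusion.** The concern holds. The only figure offered for 120 per arm describes simulated trials whose size varied, not this design. If the planning rates are true, the final analysis passes P(OR_RE<1|data)>0.95 with probability about 57% at 120 evaluable per arm, some 18 percentage points below the quoted 75%. It would be lower if 120 is the number randomised: about 52% to 42% for assumed losses of 10% to 30%. None of the fixed-size variants tried at the 0.95 threshold reaches 75% at 120 per arm.

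The 57% rests on the unadjusted two-arm model and on independent binomial outcomes at the planning rates. The choice between SD and variance for 0.843 moves it by less than half a point, and the adjusted runs stayed within about 55–57%. That the sponsor's simulation was sequential is inferred. That 75% is not the fixed-design probability does not depend on that inference.

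This should be corrected, but no planned analysis, decision or enrolment target depends on it.

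**What to change.** In Protocol 11.2, the synopsis and SAP 2.2, replace the 75% sentence with wording such as:

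> With 120 evaluable participants per arm, true VTE rates of 13% and 22.4% and the stated prior, the probability that P(OR_RE<1|data)>0.95 at the final analysis is about 57% (unadjusted two-arm model). If 10%, 20% or 30% of randomised participants have no evaluable primary endpoint (assumed range), it is about 52%, 48% or 42%.

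Add that 120 per arm is the number randomised, not the number expected in mITT. The sponsor may prefer to report its own figure from the planned three-arm adjusted model and its own expected loss rate; the adjustment should move the result by only a few points.

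If the 75% is kept, state the simulation's look schedule, maximum sample size and denominator, and say that it is not the probability for the fixed design.

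The cost is wording in three places and a less favourable headline figure. Enrolment need not change.
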